6.2.2 Recruitment Procedure

To best understand the real-world effectiveness and safety of faricimab for treatment of nAMD and DME, treating physicians are requested to ensure adequate enrollment among both anti-VEGF naïve patients and patients pre-treated with anti-VEGF so that a sufficient number of treated eye data within each sub-cohort of interest are available for analysis.

Treating physicians will explain the study to patients, addressing any questions or concerns. Treatment decisions will be determined by the treating physician and must be made independently of the patient's decision to participate in this study. When required by local regulations, the physician decision to treat with faricimab must be documented prior to the patient's enrollment.

6.2.3 Dosage, Administration, and Compliance

The dosing and treatment duration of faricimab received by participants of this NIS is at the discretion of the treating physician, in accordance with local clinical practice and local labeling.

6.2.4 Concomitant Medication and Treatment

Concomitant treatment is at the discretion of the treating physician, in accordance with real-world clinical practice. Concomitant medications (ocular and non-ocular) prescribed in this study at the beginning of the observation period or introduced during the observation period will be documented in the eCRF at index date and throughout the study, if applicable.

6.3 VARIABLES

The data collection overview is presented in [Table 1](#). The data collection schedule is presented in [Appendix 2](#), which outlines variables that will be collected at index date, enrollment (incl. retrospective data) and during follow-up.

The eCRF will serve as the primary reference for information regarding parameters collected in the study.

Table 1: Variables to be Collected in this Study

Category	Variable
Demographic characteristics at enrollment	
 ● Year of birth ● Sex (Female, Male, Other) ● Smoking status (Current Smoker, Former Smoker, Never Smoker)
Specific baseline characteristics (disease information ^a) at index date	
 ● Type of disease (nAMD, DME) and date of diagnosis (month/year) ● For nAMD patients: 
 ○ Duration of disease before study inclusion ○ Type of membrane (1-3 MNV, polypoidal choroidal vasculopathy (PCV), cystoid macular edema (CME)) ○ Pigment epithelial detachment (PED)^c or disruption within the retinal pigment epithelium ○ Duration of the disease ○ Presence/absence of atrophy^b ○ Presence/absence of fibrosis^d ● For DME patients: 
 ○ Severity of diabetes (HbA1c) ○ Duration of diabetes (date of diagnosis) ○ Diabetes type ○ Duration of DME ○ DME classification (non-central or central involvement). Central is defined as central 3 mm ○ Presence/absence of proliferative diabetic retinopathy ○ Presence/absence of ERM in the central 3 mm
Relevant medical history (ocular - by eye where applicable)	
 ● Ocular comorbidities ● Non-ocular comorbidities ● Previous intravitreal treatments (IVT) other than anti-VEGF and other ocular treatments ● Surgical history: macular laser, surgical procedures, corneal transplant, cataract surgery vitrectomy, YAG laser treatment, peripheral laser treatment, cornea surgery, steroid implant
Prior treatment and management (by eye) for health economic analysis perspectives (for eyes with previous anti-VEGF treatment)	
 ● Type of intravitreal anti-VEGF treatments received before index date. ● Date of first anti-VEGF treatment ● Time spent on each pre-treatment. ● Number of previous injections for previous treatments ● Treatment interval of the last preceding anti-VEGF treatment before entering the study.
Treatment and management (by eye) for health economic analysis perspectives (pre-treated and treatment naïve eyes), from index date until end of study	
 ● Treatment regimen (i.e., Fixed regimen, T&E, PRN, Other) ● Number of injections per eye per year per indication (nAMD, DME). ● Total number of visits, number of visits with or without treatment (observational), and time intervals between treatments, per year.
Treatment and management (by eye) during study period, from index date until end of study	
 ● Treatments received for the indications nAMD, DME (type of treatment: anti-VEGF injection, laser therapy, corticosteroid injections or steroid implants), with date of therapy. ● Therapy switch: (date and reason)

Category	Variable
	
 ● Treatment discontinuation/termination (date and reason) ● Details of other procedures that could potentially elevate/deteriorate visual acuity (VA) ● Treatment regimen (Fixed regimen, T&E, PRN, Other) ● Number (dates) of injections ● Number of loading dose intravitreal injections (per eye) ● Number (dates) of visits with and without treatment (observational) ● Treatment intervals of Q8W, Q12W, Q16W and other ● CST over time (as measured per local standard clinical practice), by eye, (including method, software settings and type of OCT) ● Eyes with presence of IRF ● Eyes with presence of SRF ● Eyes with presence of serous PED, height of PED (if measured) ● Eyes with presence of atrophy^b ● Eyes with presence of fibrosis ● Eyes with presence of hemorrhage ● Eyes with presence of ERM
Concomitant medications (ocular and non-ocular), from index date until end of study	
 ● Ocular concomitant medications (type, indication and treatment time) ● Non-ocular concomitant medication (type, indication and treatment time)
Visual acuity (VA) by eye, from index date until end of study	
 ● VA (as measured per local clinical practice) including method of VA assessment - scale and type of correction (e.g., Best-corrected, Corrected, Pinhole, Uncorrected), and date of assessment.
Imaging assessments (by eye) as per routine clinical practice (during visits for the retinal indications), from index date until end of study Note: Diagnostic images for this study will not be stored, hence assessment of images by investigators must be well-defined.	
 ● Optical coherence tomography (OCT)-imaging assessment type (e.g. SD-OCT, SS-OCT), machine used ● Results, including: 
 ○ SRF assessment (presence/absence) ○ IRF assessment (presence/absence) ○ CST assessment (numerically) ○ Serous PED assessment (presence/absence and height of PED if measured)
Safety events (all ocular and non-ocular AEs), from index date until end of study	
 ● Type of AE: 
 ○ AE/SAE ○ AESI ○ Ocular/non-ocular ● Onset date and resolution date ● Outcome ● Seriousness ● Severity ● Action taken ● Relationship to therapy (i.e., related or unrelated) ● For ocular events: eye(s) affected

AE = adverse event, AESI = adverse events of special interest, anti-VEGF = anti-vascular endothelial growth factor, CME = cystoid macular edema, CST = central subfield thickness, DME = diabetic macular edema, ERM = epiretinal membrane, HbA1c = Hemoglobin A1c, IRF = intraretinal fluid, IVT = intravitreal treatment,

MNV = macular neovascular membrane, nAMD = neovascular age-related macular degeneration, OCT = optical coherence tomography, PCV = polypoidal choroidal vasculopathy, PED = pigment epithelial detachment, PRN = pro re nata, RPE= retinal pigment epithelium, SAE = serious adverse event, SD-OCT = spectral domain optical coherence tomography, SRF = subretinal fluid, SS-OCT= swept-source optical coherence tomography, T&E = treat-and-extend, VA = visual acuity, YAG laser = yttrium aluminum garnet laser

^a To be assessed as per the treating physician.

^b Atrophy definition: Defined as cRORA (complete loss of photoreceptors and the RPE) in the central 3 mm), atrophy is to be assessed as per the treating physician (Sadda S et al 2018, Guymer RH et al 2020, Savastano MC et al 2020).

^c Serous PED: Separation between the RPE and the inner most aspect of Bruch's membrane. Is to be evaluated in the central 3 mm.

^d Fibrosis: Hyperreflective material below the neurosensory retina on OCT (may have a multilaminar appearance) accompanied by different amounts of RPE destruction & photoreceptor loss. It is to be evaluated by the treating physician in the central 3 mm (Willoughby AS et al 2015, Gräfe MGO et al 2020).

6.3.1 Visual Acuity

The primary effectiveness variable is VA. VA will be collected at index date and at all available follow-up measurements. Information on the scale and type of correction (e.g., Best-corrected, Corrected, Pinhole, Uncorrected) during assessment, and the date of assessment, will be collected for each VA assessment, as available per routine clinical practice. If possible, and within routine clinical practice, it is recommended that the patient is assessed in the same manner across visits.

VA will be collected as measured per local practice and will then be converted automatically in the eCRF to the approximate ETDRS letter score ([Gregori et al., 2010](#)). Details of the conversion to approximate ETDRS letter score are outlined in [Appendix 3](#).

6.4 DATA SOURCES

Patients' data will be recorded in the database via eCRFs and stored in the electronic data capture (EDC) system. All clinical data will be processed and stored in a database. All data will be pseudo-anonymized, and each patient will have a unique code so that the information of the same patients can be linked.

6.4.1 Collection of Data on the eCRF

Patients' data will be recorded on eCRFs. The degree of detail and completeness of data collected is dependent on local clinical practice. Data from patient medical records should be entered on the eCRF as soon as they become available.

6.4.2 Data Collected During the Observation Period

During the observational period, assessments are routinely performed in accordance with current guidelines and local standard of care. When performed during the observational period, available results will be documented in the eCRF.

Please see [Appendix 2](#) for the data collection overview (as per standard of care).

6.4.3 Safety Data Collection

Clinical AEs serious and non-serious will be recorded in the eCRF during the entire observation period, with physician's assessment of severity (mild, moderate, severe) and

relationship to therapy (i.e., related or unrelated), defined by the International Organization for Standardization (ISO) Adverse Event Categorization Guidelines as described in [Appendix 4.3.15](#).

6.5 PATIENT, STUDY AND SITE DISCONTINUATION

6.5.1 Patient Discontinuation

Patients have the right at any time and for any reason to withdraw their consent to have data collected and used for the study.

Patients starting participation in a Roche Patient Support Program (PSP) after enrollment in this study will have to be evaluated for future participation in the study by the Medical Monitor in order to ensure that the PSP will not have any influence on the treatment choice of the treating physician.

Reasons for discontinuation include, but are not limited to, the following:

- Patient withdrawal of consent at any time
- Patient is entering an investigational ophthalmology clinical trial
- Patient is no longer attending the participating site
- AE
- Death

6.5.2 Discontinuation from Treatment with Studied Medicinal Product

The decision for treatment discontinuation lies with the treating physician and is not regulated by this protocol.

If a patient discontinues from faricimab treatment or switches to another treatment, even if faricimab is not being received in either eye, the patient should continue to participate in this study until the end of study participation (defined in [Section 6.1.1](#)).

6.5.3 Study and Site Discontinuation

Roche has the right to terminate this study at any time. Reasons for terminating the study may include, but are not limited to, the following:

- Patient enrollment is unsatisfactory
- Quality or compliance issues at the site

Roche will notify the physician if the study is placed on hold, or if the study is discontinued.

Roche has the right to discontinue a site at any time. Reasons for discontinuation of a site may include, but are not limited to, the following:

- Recruitment is unsatisfactory
- Poor study protocol adherence
- Inaccurate or incomplete study data recording

- Non-compliance with the Guidelines for Good Pharmacoepidemiology Practice (GPP) or any other pertinent local law or guideline

6.6 DATA MANAGEMENT

6.6.1 Data Quality Assurance

A contract research organization (CRO) will be responsible for the data management of this study, including quality checking of the data. Data will be collected in the eCRF via EDC. Sites will be responsible for data entry into the EDC system. In the event of discrepant data, the CRO will request data clarification from the sites, which the sites will resolve electronically in the EDC system.

The CRO will perform oversight of the data management of this study. The CRO will produce eCRF specifications for the study based on the Roche templates, including quality checking to be performed on the data.

All clinical data will be processed and stored in a database.

The eCRFs and correction documentation will be maintained in the EDC system's audit trail. System backups for data stored at the CRO and records retention for the study data will be consistent with the CRO's standard procedures. The CRO will comply with the Roche procedures regarding archiving and record management.

6.6.2 Electronic Case Report Forms

A study designated EDC system will be used. Sites will receive training and have access to a manual for appropriate eCRF completion. The eCRFs will be submitted electronically and should be handled in accordance with instructions from the CRO.

All eCRFs should be completed by designated trained site staff. The eCRFs should be reviewed, electronically signed, and dated by the physician or a designee.

At the end of the study, the physician will receive the data related to patients from his or her site in an electronically readable format (e.g., on a compact disc). Data must be kept with the study records. Acknowledgment of receipt of the data is required.

6.6.3 Source Data Documentation

The Site Operations Representatives will perform ongoing source data verification (SDV) as defined in the Clinical Monitoring Plan to confirm that critical protocol data (i.e., source data) entered in the eCRF by authorized site personnel are accurate, complete, and verifiable from source documents (where applicable).

Source documents (paper or electronic) are those in which patient data are recorded and documented for the first time. They include, but are not limited to, hospital records, clinical and office charts, laboratory notes, memoranda, evaluation checklists, pharmacy dispensing records, recorded data from automated instruments, copies of transcriptions that are certified after verification as being accurate and complete, microfiche, photographic negatives, microfilm or magnetic media, x-rays, patient files and records kept at pharmacies, laboratories, and medico-technical departments involved in the clinical study.

Before study initiation, the types of source documents that contain study-relevant information will be defined in the Clinical Monitoring Plan.

Source documents that are required to verify the validity and completeness of data entered in the eCRF must not be obliterated or destroyed and must be retained per the policy for retention of records described in [Section 6.8.4](#).

To facilitate SDV, the physicians and institutions must provide the MAH, and the Clinical Research Associates belonging to the contacted CRO, direct access to applicable source documents and reports for study-related monitoring, MAH audits, and IRB/EC review. The participating sites must also allow inspection by applicable health authorities.

6.7 STATISTICAL CONSIDERATIONS

Analyses will be performed using available data; however, due to the real-world, observational nature of this study, missing values are expected. Missing data will not be imputed unless otherwise specified in the SAP.

This is a NIS designed to collect RWD. It is expected that visits will not occur at a set schedule. Where applicable, to evaluate specified outcomes over time, analysis time points (e.g., 3, 6, 12, 24 months) will be defined. The listed time points are selected time points of interest; other time points may be specified in the SAP. Windowing of the visits will be relative to the time points of interest (i.e., \pm number of days from time point of interest).

Unless otherwise specified, statistical analyses will be performed per cohort and per sub-cohort.

The following 2 cohorts will be defined and analyzed:

- Cohort 1: Patients receiving faricimab for nAMD in at least one eye.
- Cohort 2: Patients receiving faricimab for DME in at least one eye.

Within each cohort, 2 sub-cohorts will be defined (treatment naïve and pre-treated) based on treatment history at eye-level when initiating faricimab for this study as described in [Table 2](#). Schematic view of sub-cohorts is presented in [Figure 1](#) below.

Table 2: Sub-cohort Details per Cohort

Cohort 1	Cohort 2
Patients receiving faricimab for nAMD in at least one eye	Patients receiving faricimab for DME in at least one eye
A. Treatment naïve sub-cohort: Patient-eyes newly initiating faricimab intravitreal treatment* in at least one eye that has never had any anti-VEGF intravitreal treatment	A. Treatment naïve sub-cohort: Patient-eyes newly initiating faricimab intravitreal treatment* in at least one eye that has never had any anti-VEGF intravitreal treatment
B. Pre-treated sub-cohort: Patient-eyes newly initiating faricimab intravitreal treatment* after being previously treated with intravitreal anti-VEGF	B. Pre-treated sub-cohort: Patient-eyes newly initiating faricimab intravitreal treatment* after being previously treated with intravitreal anti-VEGF

DME = Diabetic macular edema, nAMD = neovascular age-related macular degeneration, VEGF = vascular endothelial growth factor

*Patient-eyes newly initiating faricimab intravitreal treatment: patient-eyes initiated treatment during 3 months prior to enrollment.

[figure not shown]

Figure 1. Schematic View of Sub-cohorts

* Estimated figure based on calculated overall Sample Size

DME = diabetic macular edema, nAMD = neovascular age-related macular degeneration

Patients may be part of several sub-cohorts as analyses will be carried out at eye-level (regardless of whether it is the right or left eye).

Patients' demographics as well as medical history will be summarized for each cohort and sub-cohort using descriptive statistics. Baseline ocular characteristics and information on prior ocular treatments will be summarized descriptively.

Patient and eye disposition will be summarized overall, by cohort and sub-cohort.

Continuous variables will be summarized descriptively using mean, median, standard deviation (SD), first quartile, third quartile, minimum, and maximum. Categorical outcomes will be summarized using numbers and percentages in each category. Corresponding 95% confidence intervals (CIs) will be provided for statistical estimates if applicable.

Detailed methodology for summary and statistical analyses of data collected in this study will be documented in the SAP.

6.7.1 Analyses Sets

The analysis sets will be defined at 2 different levels.

- Eye-level analysis set applies to data that is collected separately for each eye.
- Patient-level analysis set applies to data that is collected for each patient.

All eyes in scope of an analysis will contribute to the analysis data set for that analysis. A participant who has 2 eyes meeting the scope of the analysis will contribute data on both eyes for the analysis.

6.7.1.1 Enrolled Analysis Set / Safety Analysis Set

Patient-Level

The Enrolled Analysis Set/Safety Analysis Set- Patient-Level (EAS-PL, SAS-PL) will consist of patients who meet all inclusion and none of the exclusion criteria, and who received at least one dose of faricimab in nAMD of DME indications.

Eye-Level

The Enrolled Analysis Set/Safety Analysis Set - Eye-Level (EAS-EL, SAS-EL) will consist of eyes with indication and treatment in scope for this study from patients who meet all inclusion criteria and none of the exclusion criteria, and who received at least one dose of faricimab in nAMD of DME indications.

The Enrolled Analysis Sets in this study are identical to the corresponding Safety Analysis Sets, because according to the inclusion criteria, only patients who have received at least one faricimab injection at enrollment or prior to enrollment can be included in the study.

6.7.1.2 Effectiveness Analysis Set

Patient-Level

The Effectiveness Analysis Set - Patient-Level (EFAS-PL) will consist of patients who meet all inclusion and none of the exclusion criteria, and who received at least one dose of faricimab in nAMD of DME indications and provide data for VA at least at the index date and one post-index visit.

Eye-Level

The Effectiveness Analysis Set - Eye-Level (EFAS-EL) will consist of eyes with indication and treatment in scope of the study from patients who meet all inclusion and none of the exclusion criteria, and who received at least one dose of faricimab in nAMD or DME indications, with VA measurements at least at the index date and one post-index visit.

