To describe retinal treatment patterns throughout study period	
 ● Number and percentage of eyes in each treatment regimen (i.e., Fixed regimen, T&E, PRN, Other - see Appendix 5) at 3, 6, 12 and 24 months of observation. ● Number of intravitreal injections per eye per year per indication overall (at month 12 and 24). ● Number of intravitreal injections in loading phase** for treatment naïve and anti-VEGF pre-treated patients (per pre-treatment type) ● Total number of visits, number of visits with or without treatment (observational) at 3, 6, 12 and 24 months of observation. ● Number and percentage of eyes with treatment switch from faricimab, including reason for switch, at 3, 6, 12 and 24 months of observation for treatment naïve and pre-treated patients (per pre-treatment type).
To describe durability of faricimab treatment within different patient groups (indication, treatment naïve/pre-treated)	
 ● Number and percentage of eyes obtaining treatment intervals of Q8W, Q12W, Q16W and other at 12 months and 24 months of observation for treatment naïve and pre-treated patients (per pre-treatment type).
To evaluate the correlation/association between retinal treatment characteristics (durability and treatment patterns) and change in VA over time in nAMD and DME	
 ● Change in VA (approximate ETDRS letter score - see Appendix 3) from index date* to months 3, 6, 12 and 24, in relation to: 
 ○ Treatment regimen (Fixed, T&E, PRN, Other - see Appendix 5) ○ Number of intravitreal treatments ○ Total number of visits ○ Treatment intervals ○ Type of pre-treatment and number of previous injections for preceding regimen at index date ○ Length of diagnosis of disease at index date

CST = central subfield thickness, DME = diabetic macular edema, ETDRS = Early Treatment Diabetic Retinopathy Study, nAMD = neovascular age-related macular degeneration, PRN = pro re nata, T&E = Treat-and-Extend, VA = visual acuity, VEGF = vascular endothelial growth factor

*Index date is defined as the date of first faricimab treatment on eye-level. If both eyes are treated with faricimab and the treatment start dates are different, each start date will be used as index date for the respective eye.

**Loading phase is defined as per local label (for nAMD and DME)

Safety Objective

Safety Objective	Safety Analysis

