B. Pre-treated sub-cohort: Patient-eyes newly initiating faricimab intravitreal treatment* after being previously treated with intravitreal anti-VEGF	B. Pre-treated sub-cohort: Patient-eyes newly initiating faricimab intravitreal treatment* after being previously treated with intravitreal anti-VEGF

DME = diabetic macular edema, nAMD = neovascular age-related macular degeneration, VEGF = vascular endothelial growth factor

*Patient-eyes newly initiating faricimab intravitreal treatment: patient-eyes initiated treatment during 3 months prior to enrollment.

Patients may be part of several sub-cohorts as analysis will be carried out at eye-level (regardless of whether it is the right or left eye).

Unless otherwise specified, statistical analyses will be performed per cohort and per sub-cohort.

Patients' demographics as well as medical history (ocular and non-ocular) will be summarized using descriptive statistics. Baseline ocular characteristics and information on prior ocular treatments will be summarized descriptively.

Patient and eye disposition (e.g., enrolled, treated, switched therapy, early discontinuation, study completers) will be summarized using the Safety Analysis Sets.

Continuous variables will be summarized descriptively using mean, median, standard deviation (SD), first quartile, third quartile, minimum, and maximum. Categorical outcomes will be summarized using numbers and percentages in each category.

The primary effectiveness endpoint is the change in VA (approximate ETDRS letter score - see [Appendix 3](#)) from index date to month 12 in nAMD and DME. Both actual values at index date and month 12 and change from index date in VA (approximate ETDRS letter score - see [Appendix 3](#)) to month 12 will be summarized descriptively.

The key secondary endpoints are the change in VA (approximate ETDRS letter score - see [Appendix 3](#)) from index date to months 3, 6, and 24 in nAMD and DME, and the change in CST from index date to months 3, 6, 12 and 24 (as measured per local standard clinical practice). All primary, secondary and exploratory effectiveness outcomes will be analyzed using the Effectiveness Analysis sets.

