6 RESEARCH METHODS

6.1 STUDY DESIGN

6.1.1 Overview of Study Design

The FaReal study is a non-interventional, prospective, multinational, multicenter study designed to collect real-world data on patients treated with faricimab in nAMD and DME in the real-world routine clinical practice with primary prospective data collection (NIS PDC) and retrospective collection of prior medical/treatment history data from medical records.

Participation in this study will not change or influence a patient's standard of care in any way. The decision to start treatment with faricimab must be taken independently by the treating physician and before the decision to invite the patient into the study.

This study aims to enroll approximately 850 patients from approximately 65 sites (in 18 countries in region Europe and Israel). The expected duration of the study is approximately 4 years.

Adult patients fulfilling the eligibility criteria who sign informed consent (as required per local regulations) will be enrolled and followed up prospectively from enrollment until completion of 2 years of participation, death, withdrawal of consent, participation in an investigational ophthalmology clinical trial, early termination of the study, or discontinuation of the study site, whichever occurs first. Patients are free to withdraw participation at any time.

Retrospective data will be collected for pre-treated patients pertaining to their previous anti-VEGF treatments.

All patient visits will be conducted according to usual local clinical practice. No study-specific visits are mandated by the study protocol, no patient visits or remote consultations are mandated by the study protocol, and no additional tests will be performed on patients due to their participation in this study. Data will be collected only when patients present for their routine visits or are contacted remotely. Retrospective data from enrolled patients will be collected from the patient's medical history.

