Appendix 2 Data Collection Overview (as per Standard of Care)

Data Collection Schedule for FaReal Study

Data Collection ¹	Retrospective Data Collection	Data Collection at Enrollment Visit ⁷ / Baseline/Index Visit ⁸	Data Collected During Prospective Observational Period ⁹	
			Month 3, 6, 12 and 24 visits	Any other routine visits
Informed consent (as required per local regulations)		x		
Eligibility ²		x		
Demographic characteristics (year of birth, sex, smoking status)		x		
Disease information (including type of disease and date of diagnosis, disease characteristics) ³		x	x	x
Medical and surgical history (ocular, by eye where applicable) ³		x		
Prior treatment and management, by eye (treatment details, details of other procedures) ³	x			
Treatment and management (by eye) during study period (treatment details, treatment regimen/management plan including monitoring and injection visit intervals, planned and actual visit dates and reasons for delays if applicable, treatment switch and treatment discontinuation/termination) ³		x	x	x
Concomitant medications (ocular)		x	x	x

VA (Method of VA Assessment - Scale and Type of Correction and other assessments) ⁴		x	x	x
Imaging assessments (type, machine used, and the results) by eye, as per routine clinical practice (during visits for the retinal indications) ⁵		x	x	x
Safety events (all ocular and non-ocular AEs) ⁶		x	x	x

AE = adverse event, SAE = serious adverse event, VA = visual acuity.

1. Variables obtained according to routine clinical practice. No additional diagnostic or monitoring procedures shall be applied to the patients.
2. Signed informed consent must be obtained before any data collection.
3. Images taken as per routine clinical practice for the specified indications of interest will not be collected for this study.
4. The following will be collected from index date (i.e., date of treatment initiation with faricimab) until the end of the observational period: SAEs and non-serious AEs (including severity of all AEs and AEs of special interest).
5. Enrollment is the date the patient signs the Informed Consent Form to participate in this study.
6. Baseline is the date when a patient initiates treatment with faricimab in at least one eye. Index date is the date when treatment is initiated at the eye-level. If both eyes are treated with faricimab and the treatment start dates are different, each start date will be used as index date for the respective eye.

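### EFAS requires VA at the index date but no earlier VA is listed for collection, and treatment-pattern endpoints that need no VA are tied to the same rule

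*Protocol*

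**What the plan says.** **Set rule.** Section 6.7.1.2 makes EFAS-EL the eyes "with VA measurements at least at the index date and one post-index visit". The patient-level set has the same condition: patients must "provide data for VA at least at the index date and one post-index visit". Neither definition carries a window.

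**Index date.** The Synopsis fixes it to one event: "Index date is defined as the date of first faricimab treatment on eye-level".

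**Collection.** The Table 1 entry reads "Visual acuity (VA) by eye, from index date until end of study", and Section 6.3.1 says "VA will be collected at index date and at all available follow-up measurements". In Appendix 2, the row that begins "VA (Method of VA Assessment - Scale and Type of Correction and other assessments" has three marks (enrollment/baseline/index, month visits, other routine visits). As extracted, none is in the retrospective column.

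**No mandated assessment.** Section 6.1.1 states that "no additional tests will be performed on patients due to their participation in this study".

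**Reach.** The Synopsis states: "All primary, secondary and exploratory effectiveness outcomes will be analyzed using the Effectiveness Analysis sets". Section 6.7.2.2 puts all secondary analyses on EFAS-EL. These include injection counts, regimen, intervals between treatments, visits, switch and discontinuation. The Synopsis (Data Analysis) also says that disposition, including switched therapy and early discontinuation, is summarised on the Safety Analysis Sets.

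**The concern.** There are two linked problems.

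1. **Baseline VA.** In routine care VA may be taken at the visit where treatment is decided, with the injection on a later day. Section 6.1.1 requires that decision to precede the invitation to join, so the study cannot arrange a VA on the injection day. If the form takes VA only from the index date, such an eye has no pre-injection value in the database. Its change from index then cannot be computed, or it would have to be measured from a value taken after treatment began. Any loss would follow how a clinic organises its visits rather than chance, so it could affect who is represented as well as precision.

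2. **Endpoints that need no VA.** An injection count, an interval or a switch can be observed without any VA. Requiring both an index and a post-index VA removes eyes for a reason unrelated to the endpoint. Some of them are eyes that stop or switch and leave no later VA, which a switch or discontinuation percentage is meant to count.

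**Working it through.** **Step 1: can an SAP window supply the missing baseline?**

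- Section 6.1.1 leaves the value per time point to the SAP and gives two-sided examples (±30 and ±60 days).
- Section 6.7.2.2 uses the index date as a summary time point, so a window around it is possible.
- Table 1 and Section 6.3.1 list VA from the index date onward. On that reading the window has no pre-injection side. The only values left to the SAP are on or after the injection day, and a later value is not a baseline for change.

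Whether a pre-injection value exists is therefore settled by what is collected. The SAP can only choose among values that were collected.

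**Step 2: reproduce Table 3.** Section 6.7.6 defines precision as the full width of the 95% CI and assumes 5% drop-out.

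Width = 2 × 1.96 × SD / √(n × 0.95)

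| Sub-cohort (n) | n × 0.95 | SD 12 (Table 3) | SD 14 (Table 3) |
|---|---|---|---|
| nAMD naïve (240) | 228 | 3.12 (3) | 3.63 (3.6) |
| nAMD pre-treated (360) | 342 | 2.54 (2.5) | 2.97 (3) |
| DME naïve (100) | 95 | 4.83 (5) | 5.63 (5.6) |
| DME pre-treated (150) | 142.5 | 3.94 (4) | 4.60 (4.6) |

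The SD 14 column matches to rounding. The SD 12 column matches with coarser rounding. Table 3 is not in error.

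**Step 3: scenarios for a missing index VA.** The share q of affected eyes is not in the documents, so 10%, 20% and 30% are assumptions.

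Width = 2 × 1.96 × 14 / √(n × 0.95 × (1 − q))

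| Sub-cohort | q = 0 | q = 10% | q = 20% | q = 30% |
|---|---|---|---|---|
| nAMD naïve | 3.63 | 3.83 | 4.06 | 4.34 |
| nAMD pre-treated | 2.97 | 3.13 | 3.32 | 3.55 |
| DME naïve | 5.63 | 5.94 | 6.30 | 6.73 |
| DME pre-treated | 4.60 | 4.85 | 5.14 | 5.49 |

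For nAMD naïve at q = 20%: 228 × 0.8 = 182.4, and 54.88 / √182.4 = 4.06. Every width grows by 1/√(1 − q), which is about 5%, 12% and 20%. Like Table 3, this counts one observation per patient, whereas the endpoint is at eye level and a patient may contribute two eyes.

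**Step 4: the two denominators for switch and discontinuation.** Let N be the eyes in SAS-EL, S those that switch, m the eyes failing the VA rule, and s the switchers among those m.

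- Synopsis, disposition: S / N.
- Section 6.7.2.2: (S − s) / (N − m).

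The two agree only if s/m = S/N, that is, if eyes without the required VA switch at the same rate as all eyes. If they switch more often, the EFAS-EL figure is the lower one. The same holds for discontinuation. The documents give no values for m or s.

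**The case against.** **Same-day VA is not required anywhere.** The Protocol uses the index date loosely: Table 1 lists HbA1c and diabetes type as index-date characteristics, and these are hardly all measured on the injection day. Section 6.1.2 says VA dates are recorded and analysed in windows, and Section 6.3 makes the eCRF, which is not shown, the primary reference for what is collected. The Appendix 2 column combines enrollment and index. As enrollment may follow the first injection by up to 3 months, that column must already accept chart data. This stands. A reader might infer that affected eyes are certainly lost from every effectiveness endpoint and are beyond the SAP's reach. The documents do not support that, because the form may accept an earlier-dated VA and the SAP may count it.

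**An index VA is needed for a change-from-index endpoint.** This is true, and the EFAS rule is sound for that purpose. The problem is its fit with the listed collection period.

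**Switch and discontinuation are also reported on the Safety sets.** This is true, and it limits the harm. It also means that the same events are reported on two denominators. One common effectiveness set is a defensible convention, but it is a poor one for endpoints that do not use VA.

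**Patients stay in the study after a switch.** Section 6.5.2 says so, and a later VA would bring the eye into EFAS-EL. The exclusion is therefore limited to eyes with no post-index VA at all, or with no index VA.

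**The loss percentages are assumed.** This stands in full. The suggestion that whole sites could drop out is also not supported by anything in the documents.

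**Conclusion.** The point holds in a limited form.

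- **Collection.** As written, the collection period does not cover a pre-injection VA that the effectiveness set may need. An eye measured shortly before its first injection may therefore have no usable baseline. This assumes that the Table 1 wording is followed literally and that the eCRF takes no earlier VA, neither of which can be checked here.
- **Size.** It is unknown. Under the assumed 10% to 30% loss, widths grow by about 5% to 20%, which is modest for a descriptive study. Loss related to clinic workflow could matter more for representativeness, but this cannot be quantified. Nobody should conclude that Table 3 is wrong.
- **Denominators.** The treatment-pattern part does not depend on how the index date is read. Section 6.7.2.2 places endpoints that need no VA on a set defined by VA, and for switch and discontinuation this differs from the Safety-set summary in the Synopsis.

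**What to change.** 1. In Table 1, Section 6.3.1 and Appendix 2, have sites enter from the chart the last VA on or before the first injection of each eye, with its date, scale and type of correction, within a stated look-back. In Section 6.7.1.2, let that value count as the index VA for both effectiveness sets. The sponsor should choose the look-back; 30 days would be one option.
2. In Section 6.7.2.2 and the matching Synopsis sentence, move injection counts, regimen, treatment intervals, switch and discontinuation to the existing EAS-EL/SAS-EL. Keep EFAS-EL for the VA-change endpoints.

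**Cost.** One eCRF entry from existing records, some wording, and the amendment approval that Section 3 requires. No visit or test is added. Some index VA values will be a few days old, which the recorded date makes visible, and the tables will carry two denominators that need clear labels. The first change is worth making early, while sites still have the charts at hand.
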